**PURPOSE:**

- Correction of typographical errors in the dosing table (Table 2.1.1-2) for the suspension for subjects taking a CYP3A inhibitor.
- Removed the word “Tablet” from the title of Table 2.1.1-2 as the table includes dosing information for tolvaptan tablets and for the suspension formulation of tolvaptan.
- Updated the Clinical Management contact information on the title page and in Appendix 1.
- Correction of typographical error in Section 2.1.1 Dosing Rationale.

**BACKGROUND:**

Table 2.1.1-2 was added to this protocol with Amendment Number 3. Subsequent to the approval of Amendment Number 3, typographical errors were discovered in Table 2.1.1-2. The errors are being corrected with this protocol amendment (Amendment Number 4).

The Clinical Management contact information has been updated.

A typographical error in Section 2.1.1 Dosing Rationale has been corrected. The word “staring” has been corrected to “starting”.

**MODIFICATIONS TO PROTOCOL:**

**Sectional Revisions:** changes made to specific sections of the protocol are listed in the table below.

Location	Old Text	Updated Text
Title Page:	Clinical Management [REDACTED] Phone [REDACTED]; Fax [REDACTED]; E-mail: [REDACTED]	Clinical Management [REDACTED] Phone [REDACTED]; Fax [REDACTED]; E-mail: [REDACTED]
	Issue Date: 03 Jul 2013 Date of Amendment 1: 04 Nov 201 Date of Amendment 2: 19 May 2014 Date of Amendment 3: 26 February 2015	Issue Date: 03 Jul 2013 Date of Amendment 1: 04 Nov 201 Date of Amendment 2: 19 May 2014 Date of Amendment 3: 26 February 2015 Date of Amendment 4: 07 May 2015
2.1.1 Dosing Rationale:	... Subjects $\geq$ 2 years of age, weighing $\leq$ 30 kg and who cannot safely swallow a tablet, will receive an oral, once daily dose of tolvaptan suspension starting at 0.15 mg/kg.	... Subjects $\geq$ 2 years of age, weighing $\leq$ 30 kg and who cannot safely swallow a tablet, will receive an oral, once daily dose of tolvaptan suspension starting at 0.15 mg/kg.

### Old Text: Table 2.1.1-2

**Table 2.1.1-2 Starting Tolvaptan Tablet Doses in the Presence of Potent or Moderate CYP3A Inhibitors**

Tolvaptan Dose	Age/Body Weight (as applicable)	Potent Inhibitor	Moderate Inhibitor
0.1 mg/kg suspension a	44 wk to $<$ 2 y or $<$ 10 kg	-	0.05 mg/kg suspension
0.15 mg/kg suspension	$\geq$ 2 y, $\leq$ 30 kg	0.04 mg/kg suspension	0.8 mg/kg suspension
3.75 mg tablet	$\geq$ 10 kg to $<$ 20 kg	0.94 mL suspension	0.19 mL suspension
7.5 mg tablet	20 kg to 50 kg	1.90 mL suspension	3.75 mg tablet
15 mg tablet	$\geq$ 50 kg	3.75 mg tablet	7.5 mg tablet

aThe smallest volume of suspension that may be administered is 0.3 mL (0.3 mg), therefore dose reductions for potent inhibitors cannot be accommodated and for moderate inhibitors children weighing  $<$  6 kg cannot be accommodated.

**Updated Text: Table 2.1.1-2****Table 2.1.1-2 Starting Tolvaptan Doses in the Presence of Potent or Moderate CYP3A Inhibitors**

Tolvaptan Dose	Age/Body Weight (as applicable)	Potent Inhibitor	Moderate Inhibitor
0.1 mg/kg suspension a	44 wk to < 2 y or < 10 kg	-	0.05 mg/kg suspension
0.15 mg/kg suspension	≥ 2 y, ≤ 30 kg	0.04 mg/kg suspension	0.08 mg/kg suspension
3.75 mg tablet	≥ 10 kg to < 20 kg	0.94 mL suspension	1.90 mL suspension
7.5 mg tablet	20 kg to 50 kg	1.90 mL suspension	3.75 mg tablet
15 mg tablet	≥ 50 kg	3.75 mg tablet	7.5 mg tablet

aThe smallest volume of suspension that may be administered is 0.3 mL (0.3 mg), therefore dose reductions for potent inhibitors cannot be accommodated and for moderate inhibitors children weighing < 6 kg cannot be accommodated.

Location	Old Text	Updated Text
Appendix 1:	Phone [REDACTED]; Fax [REDACTED]	Phone [REDACTED]; Fax [REDACTED]

**ADDITIONAL RISK TO THE SUBJECT:** There is no additional risk to the subjects.

**Amendment Number:** 5

**Issue Date:** 17 Nov 2015

**PURPOSE:**

The main intent of the Amendment is to clarify administrative sections, align with current protocol templates, and incorporate recent requests from Regulatory Authorities (Food and Drug Administration [FDA]).

**BACKGROUND:**

This protocol serves as the single trial for the Pediatric Written Request with the FDA and the Pediatric Research Equity Act (PREA) requirement for the US. The FDA has agreed to the current version of the protocol and updates have been made to address further comments from the FDA, and other regulatory agencies.

**MODIFICATIONS TO PROTOCOL:**

**General Revisions:**

- Removed the neurocognition test battery. This was an exploratory endpoint and the removal of the neurocognition test battery has no impact on the safety aspects of the trial.
- Clarified dosing as dual formulations are employed: tablet and suspension.
- Alignment within the protocol descriptor sections of time points for pharmacokinetic assessments and serum sodium assessments; no change to requirement of time points or assessments.
- Clarification of Exclusion Criteria and added an exclusion criterion to reflect the suspension use and protocol template update.
- Removed reference to the extension study, 156-11-294.
- Standard Protocol template updates made to reflect Investigator's Brochure (IB) Edition 21 issuance.
- Clarified requirements for a full versus directed physical examination and neurological examination. Added a fontanelle assessment as age appropriate.
- Clarified urine vs. serum pregnancy test requirements.
- FE urate changed to FE urea throughout the protocol.
- Urine uric acid changed to urine urea throughout the protocol.
- Provided additional information related to the Tanner Staging Assessment, including an Appendix for classification reference.
- Updated the protocol template to make consistent with changes in the Phase 3 global protocol template (ie. revised definition of AE, SAE definition related to hospitalization, IRE definition, including potential DILI, Clinical lab test value changes, IMP Causality, Eliciting and Reporting AEs).
- Clarified pregnancies to be reported to INC Research instead of the sponsor.

- Clarified the time points in which nonserious and serious AEs will be followed.
- Updated list of abbreviations and references.

**ADDITIONAL RISK TO THE SUBJECT:** There is no additional risk to the subjects.

A complete redline version of this amendment showing all changes from the previous version will be produced and available upon final approval of this amendment.

Agreement

I, the undersigned principal investigator, have read and understand the protocol (including the Investigator's Brochure) and agree that it contains all the ethical, legal, and scientific information necessary to conduct this trial in accordance with the principles of Good Clinical Practices and as described herein and in the sponsor's (or designee's) Clinical Trial Agreement.

5.1.9.2	Technical Computational Details for the Analysis of the Exploratory Efficacy Endpoints	13
5.1.10	Analysis of Pharmacokinetic Parameters	14
5.2	Safety Analysis.....	14
5.2.1	Duration of Exposure to Trial Medication.....	15
5.2.2	Adverse Events	15
5.2.3	Laboratory Test Results	16
5.2.4	Vital Signs Data.....	16
5.2.5	Electrocardiogram Data	16
5.2.6	Postbaseline Concomitant Medications.....	16
5.3	Sample Size Re-estimation.....	17
6	Monitoring of Safety Data	17
7	SAP References	17

List of In-text Tables

Table 5.3-1	Sample Size Re-estimation	17
-------------	---------------------------------	----

1 Introduction

This statistical analysis plan (SAP) documents the statistical methodology and data analysis algorithms and conventions to be applied for statistical analysis and reporting of efficacy and safety data of Trial 156-08-276. All amendments to the protocol are taken into consideration in developing this SAP.

This SAP is prepared with protocol version Amendment 5, dated 17 Nov 2015.

2 Trial Objective

The primary objective is to demonstrate that tolvaptan effectively and safely increases and maintains serum sodium concentrations in children and adolescent subjects with euvolemic or hypervolemic hyponatremia.

The key secondary objective is to assess the pharmacokinetics (PK) of tolvaptan and the effect on fluid balance in children and adolescent subjects with euvolemic or hypervolemic hyponatremia.

3 Trial Design

This is an open-label, multicenter, multiple-dose, randomized withdrawal, parallel-group trial of tolvaptan in children and adolescents hospitalized with chronic euvolemic or hypervolemic hyponatremia (serum sodium < 130 mEq/L [mmol/L]) persisting despite initial standard therapy.

3.1 Treatment Phase A

All subjects will initially receive tolvaptan once daily on Days 1 and 2. If a subject's serum sodium level has not increased by at least 4 mEq/L (mmol/L) by end of Day 2, an additional day of treatment is required and is referred to as Day 2a. If subjects do not achieve an increase in serum sodium concentration of ≥ 4 mEq/L (mmol/L) on Day 2a, they will be defined as nonresponders. If subjects achieve an increase in serum sodium concentration of ≥ 4 mEq/L (mmol/L) on end of Day 2 (or 2a), they will be defined as responders.

3.2 Treatment Phase B

On Day 3, responders will be randomized to either the Early Withdrawal group or the Late Withdrawal group. Subjects in the Late Withdrawal group continue tolvaptan treatment on Days 3 and 4, subjects in the Early Withdrawal group do not receive additional tolvaptan treatment on Days 3 and 4. Nonresponders will not be randomized.

For nonresponders from Treatment Phase A, the investigator will determine if the subject is to either:

- Continue treatment with IMP for Days 3 and 4, or
- Prescribe treatment per local standard of care for Days 3 and 4.

Randomization will be stratified by age [REDACTED], serum sodium response [REDACTED], and underlying hyponatremia etiology [REDACTED]
[REDACTED]

Subjects randomized to the Early Withdrawal group will be observed to determine whether additional intervention is required to maintain appropriate serum sodium levels. Subjects whose serum sodium declines by ≥ 4 mEq/L (mmol/L) or whose overall clinical condition requires further treatment to raise serum sodium levels should be treated per local standard of care. Any intervention intended to raise serum sodium concentration during the first 48 hours of Treatment Phase B (including fluid restriction) will be defined as rescue therapy. Subjects receiving rescue therapy will be considered to have reached their clinical endpoint, and their data will be censored from that time forward.

3.3 Follow-up Phase C

All subjects will have an additional serum sodium measurement at 72 (± 4) hours post-last dose and 7 (+ 1) days post-last dose. A final safety follow-up telephone contact/visit will be performed 14 (+ 2) days post-last dose.

4 Sample Size and Power Justification

4.1 Sample Size for Efficacy

A total of 70 randomized subjects will provide 90% power to detect a treatment difference of 4 mEq/L (mmol/L) in change in serum sodium from Day 2 (or 2a) at the end of Treatment Phase A to the end of Treatment Phase B using a 2-sided alpha of 0.05. A standard deviation (SD) of 5 in change of serum sodium was used for the sample size calculation. After the end of Treatment Phase A at Day 2 (or 2a), subjects will be randomized at a ratio of 1:1 to either continue treatment with tolvaptan for 2 additional days (Late Withdrawal) or to discontinue tolvaptan treatment (Early Withdrawal). Sample size re-estimation will be conducted when 90% of the randomized subjects finish (complete or discontinue) the trial.

4.2 Sample Size for Pharmacokinetic Parameters

The sample size to establish similarity between the confidence intervals (CIs) for PK parameter estimates in adults and pediatrics is based on PK data of clearance.

To be conservative, it is assumed that the coefficient of variation (CV) of clearance is 0.42. In order to establish a 95% CI within 60% and 140% of the point estimate for the geometric mean estimate of clearance in an age group (age < 10 or \geq 10 years), under the assumption that the geometric mean estimates of clearance are equal between adult and pediatric subjects, CIs of the ratio of geometric means of pediatrics and adults will be constructed. Twenty pediatric subjects and 80 adult subjects are needed to have 90% power to establish a 95% CI of the ratio of geometric means within 0.71 and 1.40. In the actual analysis, all 81 adult subjects' data will be used.

5 Statistical Methods

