#### **Pharmacokinetic Sampling**

Blood samples for PK analysis will be obtained at 2 and 8 hours post-first dose, and at trough (24 [ $\pm 4$ ] hours post-previous

dose) on Days 1, 2, 3, and 4 for all subjects dosed with tolvaptan on Days 1, 2, 3, and 4, respectively, regardless of responder status. Pharmacokinetic profiles will be evaluated on an ongoing basis to determine variability among subjects. Based on the findings, PK sampling will continue for as long as necessary to establish suitable estimates of clearance with a 90% confidence interval (CI), similar to that observed in adult subject populations. Once these estimates are achieved, sampling will be discontinued in subsequent subjects in order to minimize blood draws in this pediatric population.
	
Subject Population:	
This trial will enroll approximately 100 male and female subjects to get approximately 70 randomized subjects aged <math>\geq</math> 4 weeks (or <math>\geq</math> 44 weeks adjusted gestational age) to < 18 years who have been diagnosed with euvolemic or hypervolemic hyponatremia (<math>< 130</math> mEq/L [mmol/L]) that persists despite initial standard background therapy (including fluid restriction and excluding a vasopressin antagonist). Age groups will be enrolled such that at least 50% of these subjects will be < 10 years old and at least 25% of subjects < 6 years old.
 
Subjects with acute hyponatremia or hyponatremia expected to resolve spontaneously will be excluded from the trial. Children with an impaired ability to sense or communicate their thirst will either be required per protocol to undergo closer in-hospital observation, laboratory and urine output monitoring, or will be excluded from the trial if this is not possible.
 
The protocol entry criteria have been designed to ensure careful selection of subjects with chronic (<math>\geq</math> 48 hours) dilutional hyponatremia (euvolemic or hypervolemic) associated with heart failure, hepatocellular disease (including cirrhosis), or syndrome of inappropriate secretion of antidiuretic hormone/other, who may benefit from treatment with tolvaptan, while excluding those who have acute or transient hyponatremia, have overt symptoms of hyponatremia requiring immediate intervention, or who are at increased risk for developing hyponatremic encephalopathy or osmotic demyelination.

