## **3.7.3      Pharmacokinetic/Pharmacodynamic Assessments**

### **3.7.3.1      Pharmacokinetic Assessments**

#### **3.7.3.1.1      Blood Collection Times**

Blood samples will be taken so that tolvaptan and metabolite concentrations can be determined. Samples will be taken at the following times:

- On Day 1 at 2 hours ( $\pm 5$  minutes) and 8 hours (concurrent with 8 h serum sodium sample) post-first dose.
- On Days 1, 2, 3, and 4 samples will be taken at trough ( $24 [\pm 4]$  hours post-previous dose) (prior to the subsequent dose), concurrent with serum sodium samples, for subjects dosed with tolvaptan on Days 1, 2, 3, and 4, respectively, regardless of status as responder/nonresponder.
- An early termination (ET) sample will be taken for any subject who is receiving tolvaptan.

On Day 2a no PK samples are taken.

For each PK blood sample collected volumes are not expected to exceed 1.2 mL. Total volume per sample may be lower depending on finalization of blood collection supplies.

Serum sodium assessments and other clinically necessary blood samples take priority; therefore, due to restrictions in allowable total daily blood volumes based on local guidelines and subject age, it may not be possible to take more than one PK sample per day. If so, the PK sampling should be changed to:

- Day 1: 2 hours postdose ( $\pm$  5 minutes)
- Day 2: 8 ( $\pm$  2) hours postdose (may be concurrent with serum sodium or other blood sampling)
- Day 3 at trough, ie, predose/24 hours post prior dose (concurrent with serum sodium sample)
- Day 4 at trough, ie, predose/24 hours post prior dose (concurrent with serum sodium sample)

The PK profiles will be evaluated on an ongoing basis to determine the variability between subjects. Based on the findings, PK sampling will continue for as long as necessary to establish suitable estimates of clearance with a 90% CI similar to that observed in the adult populations. Once these estimates are achieved, sampling will be discontinued in subsequent subjects.

For each subject all samples will be collected according to local guidelines and best practices for pediatric care. If a sample is missing due to limitations in allowable blood volumes based on local regulations or local practice this will not count as a protocol deviation.

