#### **7.1.2 Sample Size for Pharmacokinetic Parameters**

Sample size to establish similarity between the CIs for PK parameter estimates between adults and pediatrics is based on PK data of clearance. [REDACTED]

[REDACTED]. To be conservative, it is assumed that the CV of clearance is 0.42. In

order to establish a 95% CI within 60% and 140% of the point estimate for the geometric mean estimate of clearance in an age group (age < 10 or  $\geq$  10 years), under the assumption that the geometric means estimates of clearance are equal between adult and pediatric subjects, CIs of the ratio of geometric means of pediatrics and adults will be constructed. Twenty pediatric subjects and 80 adult subjects are needed to have 90% power to establish a 95% CI of the ratio of geometric means within 0.71 and 1.40. In the actual analysis, all 81 adult subjects' data will be used.

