#### **7.4.2.3 Pharmacokinetic Parameters**

Previously obtained PK data from 81 adult subjects who received a 30-mg dose of tolvaptan will be included in the analysis to show the similarity for PK parameter estimates between adult and pediatric subjects. An analysis of variance model will be performed on the natural-log transformed PK parameters using the MIXED procedure in SAS, in which only one fixed effect of subject group (pediatric and adult groups) is included in the model. The anti-logs of the difference of LS means and the confidence limits will provide the estimate and 90% CI for the ratio of the geometric means of pediatric group and adult group. Similarity of a PK parameter between pediatrics and adults will be indicated if the 90% CI for the ratio of the population geometric means is contained within the equivalence limits of 0.6 to 1.4.

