5.1.10 Analysis of Pharmacokinetic Parameters

To establish similarity between the CIs for PK parameter estimates between adults and pediatrics based on PK data of clearance, the clearance data of at least 20 pediatric subjects from this trial and 81 adult subjects from an existing tolvaptan trial will be used. An analysis of variance model will be performed on the natural log transformed PK parameters using the MIXED procedure in SAS, in which only one fixed effect of subject group (pediatric and adult groups) is included in the model. From each analysis, least squares means, their difference, and the 90% CI for their difference will be derived.

Then, the antilogs of the difference and the confidence limits will provide the estimate and 90% CI for the ratio of the geometric means of the 2 treatments (pediatric vs adult).

The similarity of PK parameter estimates between adults and pediatrics will be claimed if the 90% CI for the ratio of the population geometric means—based on the analysis of the log-transformed data—is contained within the confidence limits of 0.60 to 1.40.

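### The pharmacokinetic sample-size statement claims 90% power, but its own inputs give about 83%, and its criterion is not the similarity rule that will be applied

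*SAP*

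**What the plan says.** **Sizing.** Protocol 7.1.2 states: "Twenty pediatric subjects and 80 adult subjects are needed to have 90% power to establish a 95% CI". SAP 4.2 has the same sentence and describes these numbers as "needed to have 90% power to establish a 95% CI of the ratio of geometric means within 0.71 and 1.40". Both assume a CV of clearance of 0.42 and equal geometric means in children and adults, and both say that all 81 adults will be used in the analysis. The paragraph opens with another target, a 95% interval within 60% to 140% of the point estimate for "the geometric mean estimate of clearance in an age group", with age split at 10 years.

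**Decision rule.** Protocol 7.4.2.3 finds similarity "if the 90% CI for the ratio of the population geometric means is contained within the equivalence limits of 0.6 to 1.4". SAP 5.1.10 agrees: the 90% interval must be one that "is contained within the confidence limits of 0.60 to 1.40". The model there has one fixed effect (children versus adults) and uses "the clearance data of at least 20 pediatric subjects from this trial".

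**Sampling goal.** Blood sampling continues until there are "suitable estimates of clearance with a 90% CI similar to that observed in the adult populations" (Protocol 3.7.3.1.1; the synopsis says the same). This governs when sampling stops. It is not the test of the child-to-adult ratio.

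**The concern.** A power statement should be reproducible from the inputs printed beside it, and it should refer to the test that will be run. This one appears to fail on both counts. The stated 90% is too high for a 95% interval that must clear both 0.71 and 1.40. The interval level (95% against 90%) and the lower limit (0.71 against 0.60) are not those of the similarity rule.

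What is at stake is the justification for the 20 children. From the text, a reader cannot tell which criterion produced that number, or whether it means 20 in each age group or 20 overall. If the applied rule had been the harder one to meet, the comparison could have been undersized, so that has to be checked too.

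**Working it through.** **Inputs** (Protocol 7.1.2 and SAP 4.2): CV 0.42; 20 children; 80 adults; true ratio 1; 95% interval; limits 0.71 and 1.40; stated power 90%. In the public Protocol the text just before the CV assumption is blacked out. None of these inputs is hidden, but the documents do not say whether 0.42 is a CV on the original scale or an SD on the log scale, so both are shown.

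**Step 1. Standard error on the log scale.**
- Log SD = √ln(1 + 0.42²) = 0.4031.
- SE = 0.4031 × √(1/20 + 1/80) = 0.4031 × 0.25 = 0.1008.

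**Step 2. Distance to each limit.**
- ln 1.40 = 0.3365, and 0.3365/0.1008 = 3.34 standard errors.
- −ln 0.71 = 0.3425, and 0.3425/0.1008 = 3.40 standard errors.

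**Step 3. Power for the printed criterion.** The interval must clear both limits, so approximately

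power = Φ(3.339 − 1.960) + Φ(3.399 − 1.960) − 1 = 0.916 + 0.925 − 1 = 0.841.

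This treats the variance as known. Integrating over the estimated variance (t interval, 98 degrees of freedom) gives 83.1%, and simulation gives 83.2%. The stated 90% is not reproduced. With 81 adults the result is 83.2%. With log SD 0.42 and 80 adults it is 78.5%.

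**Step 4. Children needed for the printed criterion, with 80 adults.** 24 children give 89.6% and 25 give 90.7%, so 25 are needed (28 if 0.42 is the log SD).

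**Step 5. Which calculation gives 20?** Power with 80 adults, same exact method:

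| Calculation | 19 children | 20 children | 20 children, log SD 0.42 |
|---|---|---|---|
| As printed: 95% interval, 0.71 to 1.40 | 80.9% | 83.1% | 78.5% |
| 90% interval, 0.71 to 1.40 | 89.7% | 91.1% | 88.3% |
| 95% interval, 0.60 to 1.40 | 89.8% | 91.0% | 88.5% |
| 95% interval, upper limit 1.40 only | 89.95% | 91.1% | 88.7% |

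With log SD 0.4031, each of the last three rows makes 20 the smallest number of children that reaches 90%. With log SD 0.42, none of them reaches 90% at 20.

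**Step 6. Power of the rule that will be applied** (90% interval within 0.60 to 1.40). Here −ln 0.60 = 0.5108, which is 5.07 standard errors, so the upper limit dominates:

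approximate power = Φ(3.339 − 1.645) + Φ(5.069 − 1.645) − 1 = 0.955 + 1.000 − 1 = 0.955.

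The exact values are 95.2% with 80 adults and 95.3% with 81 (93.8% with 81 adults if 0.42 is the log SD).

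**The case against.** **The mismatch does no harm.** The sizing criterion is stricter than the decision rule in both interval level and lower limit, and sizing to a stricter criterion is conservative. Protocol and SAP agree on the rule itself. This stands, and it is why the point is minor. It does not make the 90% figure correct.

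**The PK test may never be run.** SAP 5.1 reports very low enrollment and early termination, and it limits the final efficacy analyses to summary statistics. SAP 5.1.10 falls under that heading. This also stands, and it limits the practical effect further.

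**The unit of 20 can be inferred.** The target is set for an age group and 20 follows, so 20 per age group is a natural reading, and SAP 5.1.10 gives 20 only as a minimum. That is reasonable, but SAP 5.1.10 attaches the 20 to one pooled pediatric group, so the two sections still need one clarifying phrase. Age is not ignored: Protocol 6.1 summarizes clearance by age group and assesses age effects.

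**A stronger reading to avoid.** A reader might infer that the 95% is a misprint for 90%, since that one change yields exactly 20. The documents do not support this as a conclusion. Counting power at the upper limit only also yields exactly 20 with no label changed, and so does replacing 0.71 with 0.60. The last is the least plausible slip, because 0.71 is close to 1/1.40 = 0.714 and looks deliberate. The 90% interval in the sampling sections lends little support, because it is a precision goal for ending blood draws.

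**Conclusion.** Wrong as written; severity minor. The stated 90% should be about 83%, a shortfall of about 7 percentage points (about 11 to 12 if 0.42 is the log SD). This rests on a true ratio of 1, log-normal clearance with the same variance in both groups, and a t interval that must clear both limits. The exact calculation, the approximations and the simulation all leave the figure well short of 90%.

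The source of the error cannot be determined from the text. The sizing criterion is not the similarity rule. A reader might infer that the similarity comparison is therefore undersized, but the rule that will be applied has about 95% power with 20 children and 81 adults, so that inference fails. The defect lies in the justification, not in the planned test.

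**What to change.** In Protocol 7.1.2 and SAP 4.2, do one of the following:

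1. State the power of the rule that will be applied: about 95% for a 90% interval within 0.60 to 1.40, with 20 children and 81 adults. This is the cleaner choice, because it ties the sizing to Protocol 7.4.2.3 and SAP 5.1.10.
2. Keep the 95% interval within 0.71 to 1.40 and restate its power as about 83%.

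In either case, say whether the 20 children are per age group or in total, and whether 0.42 is a CV or a log-scale SD.

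The cost is wording only: no extra samples and no change to the model or the decision rule. The drawback of option 2 is a less favorable stated figure. Only a sponsor who wanted the printed criterion at a true 90% would need more children (25 with 80 adults), and the applied rule does not require that.
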